8.2.1.4. Laboratory Safety Assessment

Hematology and blood chemistry will be drawn at the time points described in the Schedule of Activities (see **Section 1.3**) and analyzed at local laboratories. Unscheduled clinical labs may be obtained at any time during the study to assess any perceived safety concerns. Samples for hematology, blood chemistry, coagulation, pregnancy and urinalysis will be analyzed by the site's local laboratory.

Table 4. Safety Laboratory Tests

Hematology	Chemistry	Coagulation	Urinalysis	Pregnancy Test
Hemoglobin	ALT	PT or INR	color, appearance, specific gravity, pH, protein, glucose, occult blood, ketones, leukocyte esterase,	For female patients of childbearing potential, serum or urine
Hematocrit	AST			
RBC	Alk Phos			
Platelets	LDH			

Hematology	Chemistry	Coagulation	Urinalysis	Pregnancy Test
WBC	Total Protein		nitrite, bilirubin, urobilinogen	
Absolute Neutrophils	Sodium		microscopic examination of urine sediment	
Absolute Lymphocytes	Potassium			
Absolute Monocytes	Ferritin			
Absolute Eosinophils	Chloride			
Absolute Basophils	Calcium			
	Bicarbonate			
	Total bilirubin			
	d-dimer			
	Creatine (serum)			
	BUN			
	Albumin			
	C-reactive Protein (CRP)			
	Creatinine Clearance			
	Creatine Phosphokinase (CPK)			
	eGFR			
	IL-6			

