8.1.4. Unscheduled Visits

In the event that the patient will return to clinic at a time other than a regularly scheduled study visit, the visit will be regarded as an unscheduled visit. Assessments at unscheduled visits are at the discretion of the Investigator. All pertinent findings, including adverse events or changes in medications, will be noted in the patient medical records.

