### 1.1 Visit Adjustment

Visit 6 is End of Treatment (EOT) Visit, Treatment Discontinuation Visit or Early Withdrawal Visit at/before EOT. Data of visit 6 not in its visit window will be shifted to corresponding scheduled visit for analysis as in table below (marked ‘\*’). Visit name will be presented as ‘Adjusted Visit’ for the visits reallocated to its original scheduled visit or the next visit after preceding scheduled visit.

	Visit 6 to Visit 3~6
COVID-19-Related Symptoms	*
Clinical Status - NIAID 8-Point Clinical Progression Outcomes Scale	*
Laboratory Examination	*
Vital Signs, Pulse Oxygen Saturation (SpO2) and COVID-19-Related Clinical Signs	*

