## (4) For Visit Name (in Tables and Figures) and Visit Code (in Subject Data Listing):

Visit No.	Visit Description	Visit Day	Visit Name	Visit Code
1	Screening Visit	-7 ~ -1	Visit 1 (Screening)	V01
2	Treatment Visit (Day 1)	1	Visit 2 (Day 1)	V02D01T
3	Treatment Visit (Day 4)	4 ± 1	Visit 3 (Day 4)	V03D04T
4	Treatment Visit (Day 8)	8 ± 1	Visit 4 (Day 8)	V04D08T
5	Treatment Visit (Day 11)	11 ± 1	Visit 5 (Day 11)	V05D11T
6	End of Treatment (EOT)Visit (Day 14)	14 ± 1	Visit 6 (Day 14, EOT)	V06D14E
7	Follow-up 1 Visit (Day 28)	28 ± 3	Visit 7 (Day 28, F1)	V07D28F
8	Follow-up 2 Visit (Day 45)	45 ± 3	Visit 8 (Day 45, F2)	V08D45F
9	Follow-up 3 Visit (Day 60)	60 ± 3	Visit 9 (Day 60, F3)	V09D60F
	Unscheduled Visit	-	-	UV

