### 14.3.6 Laboratory Examination – Urinalysis

- 14.3.6.1 Urinalysis – <Item 1 and Unit>
- 14.3.6.2 Urinalysis – <Item 2 and Unit>
- 14.3.6.3 .... Refer to [Instructions and Abbreviations] of section 16 for the test terms

*<LB Layout 1: For Continuous Laboratory Test; Clinical relevance analyses will be excluded if not applicable>*

Population: Safety Population

Characteristics	Treatment Group	Difference	p-value
. Repeat Visit: No ‘Visit 1 (Screening)’ for IL-6: Visit 1 (Screening), Baseline, Adjusted Visit 3 (Day 4), Adjusted Visit 4 (Day 8), Adjusted Visit 5 (Day 11), Adjusted Visit 6 (Day 14, EOT), Visit 7 (Day 28, F1), Visit 8 (Day 45, F2)			
N (Missing)	XXX (XXX)		
Mean (SD)	XXX (XXX)		
Median (IQR)	XXX (XXX)		
Q1~Q3	XXX~XXX		
Min~Max	XXX~XXX		
		T/W <Baseline Only>	
		0.XXXX	

For W, normality is not applied <Baseline Only>

Groups Diff	§C - §S
Median (Asymptotic SE)	XXX
95% CI (HL)	XXX~XXX

Characteristics	Treatment Group	Difference	p-value
For T, normality is applied <Baseline Only>			
Groups Diff		§C - §S	
Mean (SD)		XXX (XXX)	
95% CI		XXX~XXX	
N (Missing)	XXX (XXX)		
Normal	XXX (XX.X%)		
NCS	XXX (XX.X%)		
CS (Medical History)	XXX (XX.X%)		
CS (Adverse Event)	XXX (XX.X%)		
. Repeat [Visit – Baseline] excluding Visit 1 (Screening) and Baseline			ANCOVA/W
N (Missing)	XXX (XXX)		0.XXXX
Mean (SD)	XXX (XXX)		
Median (IQR)	XXX (XXX)		
Q1~Q3	XXX~XXX		
Min~Max	XXX~XXX		
95% CI (WI)	XXX~XXXwt		
For W, normality is not applied			
Groups Diff		§C - §S	
95% CI (HL)		XXX~XXX	
For ANOVA, normality is applied	XXX (XXX)		
LsMean (SE)	XXX~XXX		
95% CI of LsMean			
Groups Diff. (T)		§C-§S	
Difference of LsMean		XXX	
95% CI of LsMean		XXX~XXX	
ANCOVA Model (p-value 0.XXXX) with effect Treatment (p-value 0.XXXX), Baseline (p-value 0.XXXX), Treatment*Baseline (p-value 0.XXXX).			
. Repeat [<Baseline> to <Visit>]			
N (Missing)	XXX (XXX)		
Relieved	XXX (XX.X%)		
Unchanged	XXX (XX.X%)		
Worsened (Medical History)	XXX (XX.X%)		
Worsened (Adverse Event)	XXX (XX.X%)		

For Item excluding IL-6 Baseline is Visit 2 (Day 1) data, or is Visit 1 if Visit 2 (Day 1) is null

For IL-6 Baseline is Visit 2 (Day 1) data

Refer to [Instructions and Abbreviations] of title pages for Transition of Clinical Relevance

**<LB Layout 2: For Categorical Urinalysis Test, including pH;  
 MHCHISQ for PH, C/F for else>**

Population: Safety Population

Characteristics	Treatment Group	p-value

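### The laboratory and vital-sign tables count scheduled visits only and have no row for patients abnormal at any post-baseline time, so some unscheduled safety results are seen only in listings

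*Protocol*

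**What the plan says.** Protocol 8.2.1.4 provides for extra draws: "Unscheduled clinical labs may be obtained at any time during the study to assess any perceived safety concerns". Under Protocol 8.1.4, when a patient returns outside the schedule, "the visit will be regarded as an unscheduled visit", and "Assessments at unscheduled visits are at the discretion of the Investigator".

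Item (4) of the SAP instructions is headed "For Visit Name (in Tables and Figures) and Visit Code (in Subject Data Listing". Its last line, "Unscheduled Visit", has a dash under visit name and the code UV. By that heading, unscheduled visits have a label for listings and none for tables.

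The continuous laboratory layout, the categorical urinalysis layout and the vital-sign shell all repeat over Screening, "Baseline, Adjusted Visit 3 (Day 4), Adjusted Visit 4 (Day 8), Adjusted Visit 5 (Day 11") and "Adjusted Visit 6 (Day 14, EOT), Visit 7 (Day 28, F1), Visit 8 (Day 45, F2"). The Relieved, Unchanged and Worsened rows of the laboratory layouts are also given visit by visit. The only rule that moves off-schedule data is in SAP 1.1, for end-of-treatment data: "Data of visit 6 not in its visit window will be shifted to corresponding scheduled visit for analysis".

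Protocol 9.8.4.3 asks for all laboratory values to be listed and for summaries by arm and time point. Protocol 8.3.1 turns laboratory or examination abnormalities that the investigator considers clinically significant, arising after first treatment, into adverse events. It keeps non-significant ones out.

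**The concern.** Safety is the primary objective, and its endpoint names laboratory and vital-sign findings. Values drawn because something looked wrong are more likely than routine ones to be abnormal, yet the shells give them no place in a laboratory or vital-sign count.

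Also, each visit is its own row, so the tables cannot show how many patients were ever abnormal on a test. Three patients abnormal once each look the same as one patient abnormal at three visits. At stake is whether a reader can compare the arms test by test without rebuilding the count from listings.

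**Working it through.** The plan states no figure for this point, so the check is a comparison of sections followed by small illustrations.

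**1. Where an unscheduled laboratory result can go**

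| Investigator's judgement (SAP instructions, items 6 and 7) | Laboratory tables | TEAE tables (14.3.1) | Listings |
|---|---|---|---|
| CS (Adverse Event) | No row | Yes, once per patient, by arm | Yes |
| CS (Medical History) | No row | Not if it is not recorded as an AE | Yes |
| NCS | No row | No (Protocol 8.3.1) | Yes |

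The second and third lines are the loss. The trial is open label (Protocol 9.5), so the judgement that puts a result in one line or another is made knowing the arm.

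The first line has a side effect. A laboratory adverse event found only at an unscheduled draw would be in the TEAE tables but not in the CS (Adverse Event) or Worsened (Adverse Event) rows of the laboratory table, with no footnote to explain the difference.

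**2. Vital signs.** Protocol 8.3.1 names examination findings and laboratory results. Vital signs enter through the primary endpoint and the grading scale in 8.3.3.1, so their route to an adverse event is less explicit. Shell 14.3.8 has no CS/NCS coding. It classes only temperature, respiratory rate, heart rate and SpO2 as Normal or Abnormal.

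**3. What by-visit rows hide.** There are six post-baseline visits (Days 4, 8, 11, 14, 28, 45) and about 20/2 = 10 patients per arm. Suppose every row shows 1/10 abnormal.
- Fewest patients ever abnormal: 1 (the same person throughout), 1/10 = 10%.
- Most: 6 × 1 = 6 (a different person each time), 6/10 = 60%.
- If visits were independent (assumed), the any-time rate is 1 − (1 − p)^6. For p = 5%, 10% and 20% this gives 26%, 47% and 74%.

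**4. A three-patient example.** Assume three patients in one arm each worsen once, independently and with equal chance at one of the four on-treatment visits. There are 4³ = 64 arrangements.
- All at different visits: 4 × 3 × 2 = 24; 24/64 = 37.5%, so the largest row shows 1.
- All at one visit: 4; 4/64 = 6.25%, so the largest row shows 3.
- Otherwise: 64 − 24 − 4 = 36; 36/64 = 56.25%, so the largest row shows 2.

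A single row shows all three in only about 1 case in 16.

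**5. Weight of one patient.** Moving an arm from 0/10 to 1/10 changes the rate from 0% to 10%. The exact (Clopper-Pearson) 95% interval changes from 0-30.8% (upper limit 1 − 0.025^(1/10)) to 0.3-44.5%.

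**The case against.** The strongest reply is that the safety tables are not all visit-based. The TEAE tables count each patient once by arm, whatever the visit, and a laboratory result judged clinically significant after first treatment has to be reported as an adverse event. This stands. A reader might infer that safety-driven results never reach any by-arm count; the documents do not support that.

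A reader might also measure the loss by the share of short abnormalities that fall between scheduled draws. That describes the sampling schedule. The SAP leaves out a value only if an extra draw was made, and the documents give no frequency for such draws.

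The exclusion is inferred from the visit lists and the dash in item (4); no sentence states it. SAP section 3 lets shaded shell text be adjusted to the data. The section 16 instructions that the shells cite, and the opening item of the instructions, are not in the text at hand. A rule there cannot be ruled out.

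The by-visit layout follows Protocol 9.8.4.3, and listings for about 20 patients can be read in full. That softens the point, but hand-counting from listings is no substitute for a stated comparison on the primary objective.

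Finally, extra draws may be ordered more often in one arm, so a row that includes them carries ascertainment bias. This stands, and the fix has to show it.

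**Conclusion.** The point holds for the laboratory and vital-sign tables, as a cheap improvement and not a flaw that undermines the safety analysis. On the shells as written, unscheduled results are in none of these tables, and no row counts patients ever abnormal after baseline. The loss is limited to unscheduled laboratory results judged NCS or CS (Medical History), unscheduled vital-sign values not recorded as adverse events, and the per-test count of patients.

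How many results are affected cannot be known from the documents. Each affected patient is worth 10 percentage points of an arm, assuming about 10 per arm. The figures in steps 3 and 4 of the working are illustrations under stated assumptions, not estimates for this trial.

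**What to change.** Keep the by-visit rows on scheduled data and make these additions.

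- **Laboratory tables with Normal/NCS/CS coding:** one row by arm, 'any post-baseline result, including unscheduled visits'. It counts patients who were Normal at baseline and NCS or CS at any later time. Show any-time Worsened (Medical History) and Worsened (Adverse Event) counts separately. A row built on Worsened alone would not do, because item (7) of the SAP instructions classes a move from Normal to NCS as Unchanged.
- **Table 14.3.8:** the same row for temperature, respiratory rate, heart rate and SpO2 only, counting patients Normal at baseline and Abnormal at any later visit. Show the denominator. Inclusion criterion 3 requires a raised respiratory rate or heart rate at entry, so few patients may start Normal on both.
- **Beside each row:** the number of unscheduled draws or measurements per arm.

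Table 14.2.4.1 already has a count of patients with any of several events that can serve as the pattern. The cost is SAP wording and one derived record per patient and test, from data already coded for listings. The downside is possible unequal ascertainment between arms, which the draw counts make visible. If the rows are not added, the SAP should at least state that unscheduled results are listed only. No clinical rule changes.

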8.2.1.5. ECG

An ECG will be done at Screening and at Day 14/EOT. It is preferable that the machine used has a capacity to calculate the standard intervals automatically, including QT and QTc interval. At each time point (see the Schedule of Activities), if the significant abnormalities (>Grade 2) in ECG intervals are revealed, then the ECGs should be re-evaluated by a qualified person at the site for confirmation as soon as the finding is made, including verification that the machine reading is accurate.

8.2.1.6. Other Assessments

To adequately monitor for the risk of 5-HT3 antagonist pre-medication which may predispose patients to arrhythmias, 24-hour telemetry monitoring for patients with electrolyte abnormalities may be performed, if clinically indicated.

8.2.1.7. Pharmacokinetics Assessments

The PK of CX-4945 will be assessed using the data collected in two CX-4945 studies.

Note: PK samples have been collected from the first four patients by the time of release of Protocol Amendment 1. PK collection is not applicable for other patients.

Table 5. PK Sample Collection Times

Day	Time
Day 1	Pre-dose*
	30 minutes post morning dose \pm 5 min.
	1 hour post morning dose \pm 5 min
	2 hours post morning dose \pm 5 min
	3 hours post morning dose \pm 10 min
	6 hours post morning dose \pm 10 min
Day 2	24 hours post Day 1 morning dose \pm 60 min*
Day 14	Pre-dose*
	30 minutes post morning dose \pm 5 min.
	1 hour post morning dose \pm 5 min
	2 hours post morning dose \pm 5 min
	3 hours post morning dose \pm 10 min
	6 hours post morning dose \pm 10 min
Day 15	24 hours post Day 14 morning dose \pm 60 min
Day 16	48 hours post Day 14 morning dose \pm 60 min
Day 17	72 hours post Day 14 morning dose \pm 60 min

*On pre-dose sampling days, the CX-4945 morning dose must be administered in the clinic.

The following PK parameters will be calculated: Cmax, Tmax, AUC_{0-T}, AUC₀₋₆, and T_{1/2}.

8.2.2. Efficacy/Anti-viral Activity Assessment

8.2.2.1. COVID-19-Related Symptom Score Assessment

Clinical Symptom Score Assessment should be completed using a Patient Reported Outcome (PRO) instrument (a Patient Diary for Assessment of Common COVID-19-Related Symptoms – see Appendix 3). Each symptom is graded from 0 to 3, sense of taste/ smell is graded from 0 to 2 (see section 1.1 and section 3 for score values). Clinical Improvement will be assessed daily during the treatment phase from Day 1 through Day 14/EOT and on Day 28 and Day 45 of the Follow-up period.

If some abnormal symptoms are not related to COVID-19 and were caused by other conditions documented in medical history and started before COVID-19, the patient can be considered as recovered, when these symptoms return to the previous (pre-COVID-19) values.

8.2.2.2. Clinical Signs Evaluation to Assess Recovery

Assessment of recovery based on clinical signs includes normalization of fever, respiratory rate, heart rate and resolution of hypoxia:

- Normalization of fever defined as $<36.6^{\circ}\text{C}$ from axillary site, or $< 37.2^{\circ}\text{C}$ from oral site or $< 37.8^{\circ}\text{C}$ from rectal or tympanic site
- Respiratory rate < 20 bpm while breathing room air with no shortness of breath
- $\text{SpO}_2 \geq 96\%$ in room air
- Heart rate <90 bpm

If some abnormal signs were caused by other conditions documented in the medical history and started before COVID-19, the patient can be considered as recovered, when these signs return to the previous (pre-COVID-19) values.

8.2.2.3. EQ-D5-5L

Administration of questionnaires for patient-reported outcomes at the time points described in the Schedule of Activities. The 5-level EQ-5D version (EQ-5D-5L) will be used to assess five dimensions: mobility, self-care, usual activities, pain/discomfort and anxiety/depression.

8.2.2.4. COVID-19 8-Point Clinical Progression Outcomes Scale

Progression is assessed on COVID-19 8-point outcomes scale at the time points described in the Schedule of Activities (Section 1.3). The ordinal scale of patient health status ranges from: 1) Death; 2) Hospitalized, on invasive mechanical ventilation or extracorporeal membrane oxygenation (ECMO); 3) Hospitalized, on non-invasive ventilation or high flow oxygen devices; 4) Hospitalized, requiring supplemental oxygen; 5) Hospitalized, not requiring supplemental oxygen - requiring ongoing medical care (COVID-19 related or otherwise); 6) Hospitalized, not requiring supplemental oxygen - no longer requires ongoing medical care; 7) Not hospitalized, limitation on activities and/or requiring home oxygen; 8) Not hospitalized, no limitations on activities.

8.2.2.5. Pulse Oxygen Saturation (SpO2):

Measuring the amount of oxygen-carrying hemoglobin in the blood relative to the amount of hemoglobin not carrying oxygen will be done at the time points described in the Schedule of Activities (see Section 1.3).

8.2.2.6. Laboratory Assessment of Changes and Trend in Inflammatory Markers

Laboratory tests for IL-6 CRP, LDH, CPK, ferritin and D-dimer levels will be done at the time points described in the Schedule of Activities (see Section 1.3) to evaluate early markers of inflammation response. Laboratory tests will be performed locally, at CLIA certified local laboratory following site's best practices.

- Ferritin levels may be useful early markers of disease progression or dysregulated immune response.
- D-dimer level is associated with pro-inflammatory cytokine cascade and development of cytokine storm.
- CRP produced by liver in response to IL-6 is a marker of inflammation and rapid increase of CRP level is a marker of increased risk of cytokine storm development.

8.2.2.7. RT-PCR

RT-PCR (nasopharyngeal swab) will be done at the time points described in the Schedule of Activities (see Section 1.3). A positive RT-PCR test (presence of SARS-CoV-2 RNA) collected within 7 days prior to Day 1 is required at screening for patient eligibility evaluation. Local, fully validated, RT-PCR tests shall be performed at screening in a CLIA-certified and CAP-accredited laboratory.

8.3. ADVERSE EVENTS (AES) AND SERIOUS ADVERSE EVENTS (SAEs)

The Investigator is responsible for the detection and documentation of events meeting the criteria and definition of an AE or SAE, as provided in this protocol. During the study when there is a safety evaluation, the Investigator or site staff will be responsible for detecting, documenting and reporting AEs and SAEs as detailed in this Section of the protocol.

8.3.1. Definitions of AE

An AE is defined as any unfavorable or unintended sign, symptom, or disease that occurs or is reported by the patient to have occurred, or a worsening of a pre-existing condition. An AE may or may not be related to the study treatment.

AEs will be elicited through direct questioning and patient reports. Any abnormality in physical examination findings or laboratory results that the investigator believes is clinically significant (CS) to the research patient and that occurred after initiation of the first study treatment will be reported as AEs. Abnormal findings that are NOT clinically significant should not be recorded as an AE.

8.3.2. Definition of SAEs

A SAE is defined as any AE that:

- Results in death
- Is life threatening (the patient is at immediate risk of dying from the AE)
- Requires patient hospitalization or prolongs existing hospitalization
- Results in persistent or significant disability/incapacity
- Is a congenital anomaly/birth defect

Important medical events that may not result in death, be life-threatening, or require hospitalization may be considered a SAE when, based upon appropriate medical judgment, they may jeopardize the patient or patient and may require medical or surgical intervention to prevent one of the outcomes listed in this definition.

8.3.3. Classification of AEs

8.3.3.1. Severity of AE

As study population is outpatients with moderate COVID-19, a standardized toxicity grading scale is modified to reflect the study population. Toxicity Grading Scale for Healthy Adult and Adolescent Volunteers Enrolled in Preventive Vaccine Clinical Trials will be used for grading AEs associated with systemic (general) abnormalities, vital signs, illnesses and lab abnormalities. Full guidelines may be obtained at <https://www.fda.gov/media/73679/download>.

Table 6. Toxicity Grading General Guidelines

Grade	Description
Grade 1	Mild; No interference with activity
Grade 2	Moderate; Some interference with activity not requiring medical intervention
Grade 3	Prevents daily activity and requires medical intervention
Grade 4	Potentially Life-threatening ER visit or hospitalization
Grade 5	Death related to AE.

8.3.3.2. Causality Assessment

AEs will be assigned a relationship (causality) to the study treatment. The Investigator will be responsible for determining the relationship between an AE and the study treatment. The type of event, organ system affected, and timing of onset of the event will be factors in assessing the likelihood that an AE is related to the study treatment. Relationship of AEs to study treatment will be classified as follows:

- 1. Definitely related:** This category applies to those AEs that the Investigator feels are incontrovertibly related to the study treatment. An AE may be assigned an attribution of definitely related if or when it meets all of the following criteria: (1) it follows a reasonable temporal sequence from administration of the study treatment; (2) it could not be reasonably explained by the known characteristics of the patient's clinical state, environmental or toxic factors, or other modes of therapy administered to the patient; (3) it follows a known response pattern to treatment with the study treatment.
- 2. Probably related:** This category applies to those AEs which, after careful medical consideration at the time they are evaluated, are felt with a high degree of certainty to be related to the study treatment. An AE may be considered probable if or when (must have three): (1) it follows a reasonable temporal sequence from administration of the study treatment. (2) It could not readily have been produced by patient's clinical state, environmental or toxic factors, or other therapies administered to the patient. (3) Disappears or is decreased upon discontinuation of the study treatment. (4) It follows a known response pattern to treatment with the study treatment.
- 3. Possibly related:** This category applies to those AEs which, after careful medical consideration at the time they are evaluated, are judged unlikely but cannot be ruled out with certainty to the study treatment. An AE may be considered possible if or when (must have two): (1) it follows a reasonable temporal sequence from administration of the study treatment. (2) It could not readily have been produced by patient's clinical state, environmental or toxic factors, or other therapies administered to the patient. (3) Disappears or is decreased upon discontinuation of the study treatment. (4) It follows a known response pattern to treatment with the study treatment.
- 4. Unlikely related:** In general, this category can be considered applicable to those AEs which, after careful medical consideration at the time they are evaluated, are judged likely to be unrelated to the study treatment. An AE may be considered unlikely if or when (must have two): (1) it does not follow a reasonable temporal sequence from administration of the study treatment. (2) It could not readily have been produced by patient's clinical state, environmental or toxic factors, or other therapies administered to the patient. (3) Disappears or is decreased upon discontinuation of the study treatment. (4) It does not follow a known response pattern to treatment with the study treatment.
- 5. Unrelated:** This category applies to those AEs which, after careful consideration at the time they are evaluated, are clearly and incontrovertibly due to extraneous causes (disease, environment, etc.) and determined with certainty to have no relationship to the study treatment.

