8.3.4. Reporting of AEs

Report initiation for all AEs and SAEs will begin at the time of the first treatment visit and continue until the end of final study visit. All events will be followed to resolution or until the patient completes the study. A final assessment of outcome will be made at that time.

All AEs must be recorded in the patient's study records. AEs will be reported using customary medical terminology along with the following information: the onset and end dates, whether the event is considered to be a SAE (see Section 8.3.2), the impact the event had on study treatment (see Section 8.3.4.1), the grade (intensity) of the event (see Section 8.3.3.1), the causality of the event (see Section 8.3.3.2), whether treatment was given as a result of the event (see Section 8.3.4.2), and the outcome of the event. (see Section 8.3.4.3).

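### Two of the four criteria for an Unlikely related AE keep the wording of evidence for causation, so the category contradicts its own description (minor; two negations correct it)

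*Protocol*

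**What the plan says.** Protocol section 8.3.3.2 gives Probably and Possibly the same four criteria, all worded as evidence for causation: plausible timing, no other ready explanation, improvement on stopping, and a known response pattern. Probably needs three. For Possibly, the text is "An AE may be considered possible if or when (must have two".

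Unlikely is described as covering AEs that "are judged likely to be unrelated to the study treatment", and its rule is "An AE may be considered unlikely if or when (must have two". Its list runs in the same order. The first half reads "1) it does not follow a reasonable temporal sequence from administration of the study treatment. (2) It could not readily have been produced by" the patient's condition or other therapies. The second half reads "3) Disappears or is decreased upon discontinuation of the study treatment. (4) It does not follow a known response pattern". So (1) and (4) are reversed, while (2) and (3) are not.

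The SAP footnotes to Tables 14.3.1.1, 14.3.1.3 and 14.3.1.5 count Definitely, Probable and Possibly as treatment-related and leave Unlikely out. Table 14.3.1.8 defines a SUSAR as an unexpected treatment-related SAE. Relationship to study therapy is one attribute of the primary endpoint (protocol section 3).

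**The concern.** The absence of another cause, or improvement when treatment stops, cannot be evidence that an AE is probably unrelated. The neighbouring Unrelated category confirms the intended direction, since it is for AEs that clearly have an extraneous cause. The pattern looks like a list copied from Possibly in which only two of the four items were reversed.

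Possibly versus Unlikely is where the SAP divides related from not related. A faulty rule there exposes the treatment-related tables and the SUSAR table. The trial is open-label, so investigators judge causality knowing the arm, and the written criteria are what should keep that judgement consistent. All-AE incidence, severity, seriousness and timing do not depend on these criteria.

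**Working it through.** No figure in the plan needs reproducing. The check is a complete enumeration of the criteria.

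**Inputs (protocol section 8.3.3.2).** Code each sign 1 if present and 0 if absent: a = plausible timing, b = no other ready cause, c = improves on stopping, d = known pattern. A pattern is written abcd, and there are 2 × 2 × 2 × 2 = 16.

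**Rules, reading a required number as at least that number.**
- Possibly: a + b + c + d ≥ 2 (11 patterns).
- Probably: a + b + c + d ≥ 3 (5 patterns).
- Unlikely as written: (1 − a) + b + c + (1 − d) ≥ 2.
- Unlikely with (2) and (3) negated: (1 − a) + (1 − b) + (1 − c) + (1 − d) ≥ 2.

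| Signs present | Meets | Score on Unlikely as written | Score after negation |
|---|---|---|---|
| 0 | – | 0000: 2 | 4 |
| 1 | – | 1000: 1; 0100: 3; 0010: 3; 0001: 1 | 3 |
| 2 | Possibly | 0011: 2; 0101: 2; 0110: 4; 1001: 0; 1010: 2; 1100: 2 | 2 |
| 3 | Possibly, Probably | 0111: 3; 1011: 1; 1101: 1; 1110: 3 | 1 |
| 4 | Possibly, Probably | 1111: 2 | 0 |

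**Effects of the missing negations.**
- 1111 and 0000 both score 2, so the criteria cannot tell them apart. After negation they score 0 and 4.
- 0110 (no other ready cause and improvement on stopping, but without plausible timing or a known pattern) meets all four Unlikely criteria. After negation it scores 2.
- Probably and Unlikely together: 0111, 1110 and 1111, which is 3 of 5. After negation, 0 of 5.
- Neither Possibly nor Unlikely: 1000 and 0001, which is 2 of 16. After negation, 0.

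**When (3) cannot be judged.** Treatment lasts 14 days (protocol section 4.1), but AE reporting is to "continue until the end of final study visit". For an AE that starts after treatment has ended there is no discontinuation to observe. Drop c and keep the thresholds, leaving 8 patterns abd. Possibly is met by 4 (011, 101, 110, 111). Unlikely as written, (1 − a) + b + (1 − d) ≥ 2, is also met by 011 and 110, so 2 of 4 overlap. Patterns 100 and 001 meet neither, 2 of 8. After negation both counts are 0.

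**What the negation does not cure.** Possibly and Unlikely together: 8 of 11 patterns as written, made up of the 3 Probably patterns above plus five two-sign patterns (0011, 0101, 0110, 1010, 1100). After negation all five remain and 1001 joins them, giving 6. These are two-against-two ties, and they arise because both categories ask for only two of four criteria.

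**Sensitivity to the reading.** If the required number means exactly that number, Probably/Unlikely overlap is 0 before and after, and Possibly/Unlikely overlap is 4 as written and 6 after. Patterns 1111 and 0000 still both score 2 as written.

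**The case against.** The strongest objection is that the text is guidance, not an algorithm. It says an AE may be considered for a category, and the investigator decides. For the three Probably patterns the descriptions already settle the matter: AEs that "are felt with a high degree of certainty to be related to the study treatment" cannot also be ones that "are judged likely to be unrelated to the study treatment". That stands as mitigation. It does not make the criteria right, and it does not help between Possibly and Unlikely, because Possibly is itself for AEs that "are judged unlikely but cannot be ruled out with certainty to the study treatment".

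Three stronger readings are tempting, and the documents do not support them.

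- A reader might take 8 of 11 as the size of the error. Five of those eight come from the shared two-of-four threshold and survive the negation.
- A reader might infer that treatment-related AEs will be undercounted. The overlaps do allow coding downwards. However, an AE with plausible timing only, or a known pattern only, has no matching category, and Unrelated requires certainty. An investigator may code it Possibly, which raises the count.
- A reader might infer that AEs coded Unlikely disappear from view. Protocol section 9.8.4.3 plans a TEAE summary by causality level, and section 9.7 puts all data in listings. All SAEs go to the Medical Monitor whatever their causality (section 8.3.5), so the SUSAR exposure shown by the documents is in the table.

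Two further changes might seem natural but are not recommended. A rule sending every tie to Possibly would put AEs without plausible timing (0011, 0101, 0110) there and override the investigator. Widening Possibly to any AE that cannot be ruled out with certainty would take in nearly every Unlikely AE, since only Unrelated demands certainty.

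**Conclusion.** The wording is wrong, and the error is minor. Two of the four Unlikely criteria point the opposite way from the category's description. The effect that most clearly reaches the SAP's related/not-related cut is the case where (3) cannot be judged: 2 of 4 Possibly patterns also meet Unlikely, no description separates them, and the negation removes the overlap. The Probably/Unlikely contradictions (3 of 5) and the patterns without a category (2 of 16) are also due to this error.

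These are counts of logical patterns, not of AEs. They assume yes/no answers on each criterion and the at-least reading, except where stated. The documents give no AE counts, so the real effect cannot be sized. For scale only: if about 20 patients split evenly, Arm A has about 10, and one patient whose only related AE changes code moves that arm's treatment-related incidence by 1/10, or 10 percentage points.

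The shared two-of-four threshold is a separate matter. It leaves 5 two-sign ties now and 6 after the correction, and these stay with the investigator's judgement.

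**What to change.** - Under Unlikely, remove the *not* from (2), so that it is met when the AE *could readily* be explained by the patient's condition, environmental or toxic factors, or other therapies. Reword (3) as *does not disappear or decrease* when study treatment is discontinued. State that (3) is not counted where treatment was not stopped or was not given.
- Issue this to sites as a written clarification.
- For AEs already coded, keep the investigator's code as the primary tabulation.
- Produce the by-causality TEAE summary that protocol section 9.8.4.3 already plans; no SAP mock-up shows it. Relabel its level *remotely* as *unlikely*, to match section 8.3.3.2. AEs coded Unlikely then appear beside the treatment-related count.

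The cost is two negations, one label and one planned table, with no recoding. Slightly more AEs may be counted as treatment-related. One pattern (plausible timing and known pattern, with another explanation and no improvement) meets only Possibly now and becomes a tie. The clarification cannot reach AEs already coded, and SAP section 2 expects the last subject to leave on 7-Oct-2021, so the by-causality table may do most of the work.
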